6.2.3 Dose and Fractionation

The dose and fractionation scheme utilized will be based on the location of the patient’s residual disease. For patients with:

Peripheral Tumors: Treatment will consist of 2 fractions of radiation, with a minimum of 40 hours separating each fraction. Two fractions of 10 Gy with inhomogeneity

correction will be delivered to the prescription line at the edge of the PTV for a total of 20 Gy. This will yield a total BED of 110 Gy.

Medial Tumors: Treatment will consist of 3 fractions of radiation, with a minimum of 40 hours separating each fraction. Three fractions of 6.5 Gy with inhomogeneity correction will be delivered to the prescription line at the edge of the PTV for a total of 19.5 Gy. This will yield a total BED 102.2 Gy.

6.3 Technical Factors

6.3.1 Physical Factors

Treatment radiation will consist of photon (x-ray) beams produced by linear accelerators. 6MV energies will be used under most circumstances, with energies of 15-16MV used only in a limited number (maximum of 2) beams that must travel a cumulative distance of more than 10cm through soft tissue (not lung) to reach the isocentre.

6.3.2 Minimum Field Aperture (Field Size) Dimension

A minimum field dimension of 3.5 cm is required for any field used for treatment delivery. If the minimum field exceeds the technical requirements for small lesions (<2.5 cm axial GTV dimensions or < 1.5 cm crano-caudal GTV dimension), the prescription dose is still prescribed to the edge of the defined PTV.

6.3.3 Critical Organ Dose-Volume Limits

All critical organ dose volume limits must take into account the initial dose delivered during chemoradiation. All initial chemoradiation must have been planned with 3-d CT planning. Typically, chemoradiation is given to 59.4-66 Gy and organs such as spinal cord and esophagus reach significant doses of radiation. Commonly the tolerance of spinal cord is considered to be 50 Gy (180-200cGy/fraction). Prior to boost stereotactic radiotherapy, all previous radiation plans must be reviewed with dose-volume histogram analysis to determine critical organ doses. In considering the stereotactic plan, if a minimum of 7 beams are used, each is contributing only approximately 140cgy of the

total prescribed dose. If any beam traverses a critical organ, the dose delivered will be considered and a maximum point dose to any organ considered.

Table 5.3.3 lists maximum dose limits to a point or volume within several critical organs to be considered when standard (180-200cGy) fractionation is given. Size of fraction delivered to each organ during stereotactic treatments must be considered, since not all beams will either enter or exit through a structure. Every attempt to keep entrance and exit doses of each fraction of SBRT traversing a critical organ to as close to a **maximum** of 200 cGy as possible to help estimate critical structure doses. All critical organs will be contoured and doses calculated in a standard fashion. Composite plans incorporating the initial radiotherapy and the stereotactic boost must be created to accurately assess tolerances.

7.0 Patient assessments

Assessments	Pre-Study entry ^a	1mo ^f Post SBRT	3mo ^f Post SBRT	Follow Up ^g	As Indicated
History/physical	X	X	X	X	
Pregnancy test ^b	X				
Toxicity eval ^c		X	X	X ^c	
PET-CT	X				X
CXray/CT		X ^d	X ^d	X ^d	X
PFT's ^e	X	X	X		X
CMP/CBC	X				

- a. Pre-study evaluations typically done 3-4 weeks after completion of primary chemoradiation. CT simm typically done approximately 1 week following study entry, with SBRT delivery done approximately 1 week after CT simm.
- b. Pregnancy test if indicated and not done prior to chemo-RT
- c. Toxicity evaluation through 6 months
- d. Ideally alternate CT/Chest rays on routine visits post-treatment
- e. Pulmonary function tests to include spirometry, lung volumes and diffusion capacity
- f. Approximate timeframe
- g. Routine follow-up visits scheduled as per institutional standard (strict FU scheduled not required).

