07-RAD-01-UK/P4:
Stereotactic Body Radiation Therapy for Post-chemoradiation
Residual Disease in Stage II/III Non-small Cell Lung Cancer

Principle Investigator:

[name]., Ph.D.
Department of Radiation Medicine
University of Kentucky

Medical Oncology Co-Investigators:

[name].
[name].
Department of Hematology/Oncology,
University of Kentucky

Imaging Co-Investigators:

[name].
[name].
Department of Diagnostic Radiology,
University of Kentucky

Statistical Co-Investigator:

[figure not shown]
[name].
Departments of Internal Medicine & Biostatistics
University of Kentucky Colleges of Medicine & Public Health

Study version 1.5.2 July 8, 2013

SCHEMA

Eligible patients with Stage II/III NSCLC[#]

Completed Definitive Chemoradiation to min 5940 cGy*

[figure not shown]

CT scan or PET/CT 21-30 days post chemo RT

SBRT boost

Peripheral Tumors: 1000cGy X 2 to residual primary mass

Medial Tumors: 650cGy x 3 to residual primary mass

Routine Followup with CT chest and/or chest x-ray at ~3 months

PET/CT if suspected recurrence/metastasis clinically indicated

Sample size: 42 patients

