3.1 Exclusion Criteria

1. Any other active cancer.
2. No prior malignancy is allowed except for the following: adequately treated basal cell or squamous cell skin cancer, in situ cervical cancer or other cancer from which the patient has been disease-free for 5 years.
3. Patients with other systemic illness, or have not recovered adequately from their primary treatment or who have evidence of progression of their lung cancer prior to therapy that, in the investigators opinions, would preclude their inclusion
4. Plans for the patient to receive other concomitant antineoplastic therapy while on this protocol, except at disease progression. Patients may be allowed to use bisphosphonates for hypercalcemia.

5. Pregnant or lactating women

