4.0 PRETREATMENT EVALUATIONS

(All lab tests and radiographic studies should be done at approximately 3 weeks post chemoradiation)

- 4.1** Complete history, physical examination, and evaluation of Zubrod Performance Status.
- 4.2** Pathological (*biopsy*) or cytologically proven non-small cell lung cancer.
- 4.3** Postchemoradiation CT with contrast or PET/CT (preferred) of chest and upper abdomen to include the liver and adrenals; baseline brain MRI or CT scan.
- 4.4** Bone scan, only if the patient has bone pain and/or and elevated alkaline phosphatase.
- 4.5** Pulmonary function tests - including DLCO and FEV1
- 4.6** CBC; serum chemistry tests to include alkaline phosphatase, glucose, creatinine, electrolytes, AST (*SGOT*), and total bilirubin,

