5.2.2 Dose Specification : Radiation therapy: Patients will be have CT planning designed to encompass all known disease. While mediastinal coverage is recommended, fields will be at discretion of the treating physician in accordance with standard therapy. Recommended plans will give patients initial fields using AP:PA plans to approximately 3960cGy, followed by off cord boost to a final dose of 5940 cGy or higher. Alternative plans respecting dose limiting organ tolerances would be acceptable. All patients will be treated at 180-200 cGy/day on minimum 6 mV linear accelerators or higher energies. All attempts are to be made to cover contoured GTV's by minimum a 95% of prescribed dose.

5.2.3 All patients will have 3-d planning with attention to dose limiting organs. Complete dose volume histograms must be provided and include (at a minimum) spinal cord, esophagus, brachial plexus as appropriate, combined lung volumes (to estimate V₂₀), heart, gross tumour volume (may have separate GTV's for primary tumour and nodes), planning target volume (GTV+ 1.0-2.0 cm at the discretion of the treating physician)

[figure not shown]

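### A pregnancy test from before chemoradiation can replace the entry test, with no maximum age, so the result is about 51 days old or more at entry

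*Combined protocol and SAP*

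**What the plan says.** Section 3.1 item 5 excludes "Pregnant or lactating women". The assessment table in Section 7.0 marks a pregnancy test at pre-study entry and at no later visit. Footnote b qualifies that mark: "Pregnancy test if indicated and not done prior to chemo-RT". No section sets a maximum age for the earlier result or defines when a test is indicated.

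Section 4.0 gives the timing of the entry work-up, "All lab tests and radiographic studies should be done at approximately 3 weeks post chemoradiation", but its list contains no pregnancy test. Footnote a of Section 7.0 describes the same window: "Pre-study evaluations typically done 3-4 weeks after completion of primary chemoradiation". It then places the planning CT about one week after entry and SBRT about one week after that.

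**The concern.** Footnote b joins two conditions: the test must be indicated, and it must not have been done before chemoradiation. Once a test has been done before chemoradiation, none is required at entry. That earlier result predates the whole chemoradiation course and the three to four weeks that follow, so it says nothing about a conception in that time.

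A site that follows the footnote exactly could therefore apply the pregnancy exclusion with an uninformative result. If the entry history and physical also missed an early pregnancy, the woman would go on to the planning CT and SBRT. A second, smaller gap is that, with the indication undefined, the footnote does not by itself guarantee that every woman of childbearing potential is tested at all.

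**Working it through.** The plan states no age for the test, so there is no figure of its own to reproduce. The age follows from calendar arithmetic.

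**Inputs**

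- Minimum dose, from the schema: "Completed Definitive Chemoradiation to min 5940 cGy".
- Daily dose, from Section 5.2.2: "All patients will be treated at 180-200 cGy/day on minimum 6 mV linear accelerators or higher energies".
- Usual dose range, from Section 6.3.3: "Typically, chemoradiation is given to 59.4-66 Gy".
- Wait to the entry scan, from the schema: "CT scan or PET/CT 21-30 days post chemo RT".
- Assumed: the test is taken the day before the first fraction (test on day 0, first fraction on day 1). An earlier test adds to every figure.

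**Number of fractions** = total dose / daily dose, rounded up

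- 5940/200 = 29.7, so 30
- 5940/180 = 33
- 6600/200 = 33
- 6600/180 = 36.7, so 37

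**Shortest case.** Thirty fractions on consecutive days, weekends included, put the last fraction on day 30.

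Age at entry = day of last fraction + wait = 30 + 21 = 51 days.

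The wait is only approximate in the text. A 30-day wait gives 30 + 30 = 60 days. A 14-day wait, which is an assumption shorter than anything the documents describe, gives 30 + 14 = 44 days.

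**Five fractions per week.** The documents do not give this rate, so it is an assumption. Each row covers all five weekday starts.

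| Fractions | Day of last fraction, Monday to Friday start | Age at entry, 21-day wait | Age at entry, 30-day wait |
|---|---|---|---|
| 30 | 40, 42, 42, 42, 42 | 61–63 | 70–72 |
| 33 | 45, 45, 45, 47, 47 | 66–68 | 75–77 |
| 37 | 51, 51, 51, 51, 53 | 72–74 | 81–83 |

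The overall range is 61 to 83 days, or 61 to 81 if every course starts on a Monday.

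**Age at SBRT.** Footnote a adds about 14 days: 51 + 14 = 65 days in the shortest case, and 61 + 14 = 75 to 83 + 14 = 97 days at five fractions per week.

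**The case against.** The strongest reply is that other controls already apply. The exclusion holds whatever the test schedule says, and nothing forbids a repeat test. Section 3.0 item 9 requires effective contraception, and a history and physical are done at entry. Section 1.0 puts the average age at diagnosis in the mid-60s, so harm needs a rare chain of events. Leaving the indication to the physician also matches the discretion that the protocol allows elsewhere.

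Most of this stands, and it is why the point is minor. It does not make the footnote sound. Item 9 has no start date that covers the interval between the earlier test and entry, and a history and physical can miss an early pregnancy. Eligibility begins at age 18, and the protocol itself provides for women of childbearing potential.

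A second reply is that 51 days is not a strict lower bound. The wait is described only approximately. The schema also leaves the radiation dose to the treating physician, Section 3.0 item 4 names no dose, and Section 5.2.2 presents its plan as recommended. That is fair as far as it goes: the figure is approximate. But the schema and Section 1.3 both give 59.4 Gy as the minimum, and no section describes a wait as short as 14 days. The logical gap does not depend on the exact number of days.

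**Conclusion.** The concern holds, as a minor safety point. Footnote b allows a result of unlimited age to stand in for the entry test, and that result cannot detect a conception during or after chemoradiation.

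Its age at entry is about 51 days or more. That rests on the 59.4 Gy minimum, at most 2 Gy per day, treatment seven days a week, a wait of about 21 days, and a test the day before the first fraction. At five fractions per week it is 61 to 83 days for 30 to 37 fractions. Treatment breaks, or a dose above 66 Gy, would take it past 83.

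Among the 37 to 42 planned patients the number of women affected could be zero. Sample size, the primary estimate and the stopping rule do not change.

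**What to change.** Replace footnote b with wording such as:

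> Pregnancy test required for all women of childbearing potential in the post-chemoradiation entry window, regardless of any earlier test; a negative result is needed before study entry and before the planning CT (ideally before the entry CT or PET/CT).

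Add the test to the laboratory list in Section 4.0. Done with the other entry evaluations, it would be about 0 days old at entry and about 14 days old at SBRT.

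The cost is one footnote, one added line, and one inexpensive test for a few women at a visit that already includes blood work. The clause in brackets is optional. If it is adopted, the blood draw has to be scheduled ahead of the scan; the gap is closed without it.

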8.0. Criteria for Evaluation

8.1. Response determination – This protocol will use a modified version of the international criteria proposed by the Response Evaluation Criteria in Solid Tumors

(RECIST) Committee (JNCI 92(3): 205-216, 2000). Additional definitions beyond the RECIST guidelines specific to this protocol are incorporated to define local control as defined below.

8.2 Baseline documentation of Target and Non-target lesions

The longest diameter (LD) for the target lesion will be calculated from the treatment planning CT scan using pulmonary windowing and reported as the baseline LD. The baseline LD will be used as the reference by which to characterize the objective tumor response. For follow-up assessment, diagnostic CT scans using lung windows are the preferred modality. Local treatment effects in the vicinity of the tumor target may make determination of tumor dimensions difficult e.g. patchy consolidation.

All other lesions which appear or enlarge after treatment e.g. regional lymph nodes and distant metastases should be identified as non-target lesions and should be recorded at the time of their appearance/suspicious enlargement. Patients who have suspicious CT scans may have PET/CT to assess local failure/distant metastasis as per clinical judgment.

8.2.1. Post treatment followup - Followup evaluation will be performed approximately 30 days after completion of all protocol treatment to assess toxicity and tumor response.

Follow-up for evaluation of toxicity will continue for 6 months following SBRT delivery. Additional follow-up for local control and survival will continue until death or study withdrawal.

8.3 Response Criteria

8.3.1 Evaluation of Target Lesions

Complete Response (CR) – disappearance of the target lesion, ideally on PET/CT although assessment by CT is acceptable.

Partial Response (PR) – At least a 30% decrease in the LD of the target lesion, taking as reference the baseline LD. Ideally this determination will be on CT evaluation.

Stable Disease (SD) – Neither sufficient shrinkage to qualify for CR/PR as above, nor sufficient increase to qualify for LE as below, taking as reference the smallest LD since treatment started.

Local Enlargement (LE) – At least a 20% increase in the LD of the target lesion

with respect to the LD based on followup

Local Failure (LF) – refers to the primary treated tumor after protocol treatment and corresponds to meeting both of the following criteria: 1. increase in tumor dimension of 20% as defined for the above LE; 2. The measurable tumor with criteria meeting LE should be avid on PET/CT with uptake of similar intensity as the pretreatment staging PET/CT

9.0 Data and Safety Monitoring Plan

The study principal investigator has primary responsibility for monitoring the safe conduct of this study. Additionally, the Markey Cancer Center Quality Assurance Committee (QAC) provides oversight and monitoring of all cancer clinical trials. The Committee is responsible for reviewing data to identify patient safety and protocol compliance issues. The Markey Protocol Review Committee (PRC) assigns studies a QAC review timeline based on the phase, origination of the study and known safety issues.

The members of the QAC consist of Medical Oncologists, a Pharmacist, a Nurse Manager, a Certified Clinical Research Professional and a Reporter. These members were selected based on their experience, reputation for objectivity and knowledge of clinical trial methodology. All members should view themselves as representing the interest of the study patients and not that of the institution.

At each meeting, representatives for each study on the agenda present their study data to the QAC for review. The Principal Investigator, CRA and/or Study Coordinator present the following data for active patients: treatment issues, serious adverse events (SAEs) per FDA's definition, dose levels, dose modifications, and responses as applicable.

The QAC will reviews protocols to assure the following:

- progress of the trial and safety of participants,
- compliance with requirements regarding the reporting of severe adverse events,
- that any action resulting in a temporary or permanent suspension of this NIH-funded clinical trial is reported to the responsible NIH grant program director, and

- data accuracy and protocol compliance.

The QAC, the Protocol Review Committee (PRC), the responsible disease-specific Clinical Care and Research Team (CCART) and/or the UK/VA IRB are empowered to immediately suspend accrual to any study under its purview for any of the following:

- Failure to comply with AE/SAE reporting requirements,
- poor study enrollment,
- protocol violations, or
- issues related to patient safety.

10.0 Statistical Considerations

10.1. Sample size justification :

In this pilot protocol, it is anticipated that 37 patients will be enrolled to receive boost therapy. This number of patients will provide a 10% level of precision (half-width of a 90% confidence interval) for the true (unknown) proportion of subjects that will experience toxicity-limiting pneumonitis. The investigators believe this proportion will be no greater than 20% and have used this number in the sample size justification based on the 90% confidence interval width.

10.2 Stopping rules for severe pneumonitis:

We anticipate that pneumonitis may be the most common radiation-related side effect, and patients will be closely monitored for development of severe pneumonitis in this study. An historical rate of severe pneumonitis rate has been documented to be as high as 15% but varies depending on the volume of lung being irradiated (12). Treatment of most stage III lung cancers carry risks in the 15% and higher range due to volumes of lung irradiated. As such, the protocol will be stopped if sufficient evidence exists suggesting that, among patients receiving therapy, the true incidence of severe pneumonitis exceeds 15%. Sufficient evidence will be statistically defined in the form of an estimate for the severe pneumonitis rate (binomial proportion) whose lower 90% confidence limit exceeds 15%, and these estimates will be made after every 5th enrolled patient to the study. Operationally, any of the following observed ratios (# experiencing severe

pneumonitis of total number observed) would lead to exceeding such a limit: 3 or more of the first 5; 4 or more of the first 10; 5 or more of the first 15; and 6 or more of the first 20.

If the true probability of severe pneumonitis incidence is 10%, the probability of stopping the study under these rules is less than 1% after enrollment of 5 patients on the study, <1.3% after enrollment of the first 10, and roughly <1% after enrollment of 20 patients on the study. If the true probability is 20%, then the probability of stopping after 5, 10, and 20 patients is 6%, 12% and 19%, respectively. If the true probability is 40%, the probability of stopping after 5, 10, and 20 patients is approximately 32%, 62%, and 88%, respectively.

11. Reporting Toxicity

11.0 All patients will be assessable for toxicity, and those with measurable disease will be assessable for response. All grade 4 or grade 5 toxicities that are attributable to radiation therapy will be reported to the DSMB and Institutional Review Board within 24 hours of discovery. The boost therapy is given in a two to three day period, and definitions of acute vs. late effects are used as below. Monitoring of late effects of radiation therapy (most commonly pneumonitis) will continue for 6 months following completion of the boost therapy.

11.1 *Acute Radiation Toxicity Monitoring:* Acute (\leq 90 days from RT start) side effects of radiation therapy will be documented using the NCI Common Toxicity Criteria version 3.0. A copy of the CTCAE version 3.0 can be downloaded from the CTEP homepage (<http://ctep.info.nih.gov>).

11.2 *Late Radiation Toxicity Monitoring:* Late ($>$ 90 days from RT start) side effects will be documented using the NCI Common Toxicity Criteria version 3.0.

11.3 Death from any cause while the patient is receiving protocol treatment and up to 30 days after the last protocol treatment, will be reported directly to the DSMB and IRB

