2.0 Objectives

Primary

1. to determine the toxicity of the SBRT boost dose by estimating the proportion of subjects enrolled who develop pneumonitis

Secondary

1. to determine response rates of the residual primary tumor following SBRT boost

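### Thirty-seven patients do not give the stated 10% precision at a 20% pneumonitis rate, and the schema gives 42 instead

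*Combined protocol and SAP*

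**What the plan says.** Section 10.1 (Sample size justification) gives the size of the trial: "it is anticipated that 37 patients will be enrolled to receive boost therapy". It then states what that number achieves: "This number of patients will provide a 10% level of precision (half-width of a 90% confidence interval) for the true (unknown) proportion", the proportion being that of subjects with toxicity-limiting pneumonitis. On the planning value it says: "The investigators believe this proportion will be no greater than 20% and have used this number in the sample size justification".

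The schema at the front of the same document reads: "Sample size: 42 patients".

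Two other places bear on the point. The primary objective in section 2.0 is "to determine the toxicity of the SBRT boost dose by estimating the proportion of subjects enrolled who develop pneumonitis", so the sample size argument concerns the precision of a single proportion. Section 11.0 says "All patients will be assessable for toxicity", and no dropout rate, evaluability rule or replacement rule appears anywhere in the document.

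**The concern.** Section 10.1 supplies every input needed to check its own claim: a confidence level, a target half-width, a planning rate and a sample size. The four do not fit together. The schema's 42 fits much better, but the written justification is tied to 37.

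The trial has no hypothesis test and no power statement. The width of the confidence interval is the only reason given for its size, so an error there leaves the size unsupported as written.

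The two numbers also differ in practice. A reader cannot tell whether accrual ends at 37 or at 42, or which denominator the primary estimate will have. Section 10.2 schedules a pneumonitis estimate after each fifth enrolled patient, so the last one falls at 35 under one target and at 40 under the other.

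**Working it through.** **Inputs, all from section 10.1 except the last**

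- Confidence level 90%, two-sided, so z = 1.6449
- Target half-width w = 0.10
- Planning proportion p = 0.20
- Sample size n = 37 (section 10.1) or n = 42 (schema)

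**Trying to reproduce the plan's figure.** Section 10.1 does not name an interval method, so start with the normal approximation (Wald):

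half-width = z × √(p(1 − p)/n)

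- n = 37: 1.6449 × √(0.16/37) = 1.6449 × 0.0658 = 0.1082, or 10.8%
- n = 42: 1.6449 × √(0.16/42) = 1.6449 × 0.0617 = 0.1015, or 10.15%
- n = 43: 0.1003
- n = 44: 0.0992

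The stated 10% is not reproduced at 37.

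**Sample size for a 10% half-width.**

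n = z² p(1 − p)/w² = 2.7055 × 0.16/0.01 = 43.3, rounded up to 44.

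**Does another method rescue 37?** Half-widths at p = 0.20, 90% two-sided, taking the event count as 0.20 × n where the method needs one:

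| Interval | n = 37 | n = 42 | n for ≤ 10% |
|---|---|---|---|
| Wald | 10.8% | 10.15% | 44 |
| Wilson | 10.6% | 10.0% | 43 |
| Jeffreys | 10.6% | 10.0% | 43 |
| Agresti-Coull | 10.8% | 10.2% | 44 |
| Clopper-Pearson (exact) | 11.9% | 11.1% | 52 |
| Wald, continuity-corrected | 12.2% | 11.3% | 53 |

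Reading the interval as one-sided 90% gives n = 27, and a 95% level gives n = 62. No variant returns 37.

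**Whole-number event counts.** Twenty percent of 37 is 7.4, so the nearest results are 7 or 8 events.

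- Wald half-width: 10.6% at 7/37 and 11.1% at 8/37
- Exact 90% interval at 7/37: 0.092 to 0.326, half-width 11.7%
- Exact 90% interval at 8/37: 0.112 to 0.356, half-width 12.2%
- Exact 90% interval at 8/42: 0.098 to 0.318, half-width 11.0%
- Exact 90% interval at 9/42: 0.117 to 0.344, half-width 11.4%

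**At what rate would 37 be enough?** Set z² p(1 − p)/37 = 0.01. Then p(1 − p) = 0.37/2.7055 = 0.1368, so p is about 0.163. For example, p = 0.16 gives 9.9% and p = 0.17 gives 10.2%.

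**Could 42 be 37 plus attrition?** The document gives no attrition rate. If 10% is assumed, 37/0.90 = 41.1, rounded up to 42. The arithmetic works, but the 10% is an assumption, and 37 patients analysed would still give 10.8%.

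**The case against.** The strongest reply is that little depends on this. The trial is a pilot, the gap is 0.8 points, and no decision threshold uses the 10% figure. The stopping boundaries listed in section 10.2 end at 20 patients, so they are the same under either target. This is a fair account of the size of the numerical shortfall, and it stands. It does not settle which enrolment number applies.

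A second reply is that there is only one fault. If 37 in section 10.1 is an outdated or mistyped 42, then the half-width is 10.15% (Wald) or 10.0% (Wilson), which is 10% as the plan rounds it. That may be what happened, but the document does not say so, and the text still needs correcting.

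Third, the two numbers may count different groups: 42 entered and 37 boosted. The schedule in section 7.0 leaves about two weeks between study entry and SBRT, so some loss is conceivable. But section 10.1 describes the 37 as enrolled, no attrition allowance is stated, and the precision sentence fails for 37 on this reading too.

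Fourth, 20% is described as a ceiling, and at a 15% rate 37 patients give 9.7%. That limits the practical consequence. It does not rescue the sentence, because section 10.1 says 20% was the number used.

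Two points of detail are accepted. The figure of 44 belongs to the normal approximation; Wilson or Jeffreys needs 43. And section 10.1 sizes the trial for toxicity-limiting pneumonitis, while section 2.0 names pneumonitis without a grade; the calculation is the same for either at a 20% rate.

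**Conclusion.** The concern holds on both counts. From the plan's own inputs, 37 patients give a 90% half-width of 10.8% by the normal approximation, 10.6% by Wilson, and 11.7% to 12.2% by the exact method at 7 or 8 events, against a stated 10%. Thirty-seven is 7 patients (about 16%) short of the 44 that the normal approximation requires. The schema's 42 comes close to the stated precision but is not the number that section 10.1 justifies, and the two are not reconciled.

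The conclusion assumes a two-sided 90% interval and the 20% planning rate, both as section 10.1 gives them. It does not depend on the interval method, since none of the two-sided 90% methods tried reaches 10% at 37. The more important part is the unresolved enrolment target; the numerical shortfall alone is minor.

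**What to change.** State one sample size in the schema and in section 10.1, name the interval method, and give the half-width that number delivers at 20%.

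- If 42 is intended, change 37 to 42 in section 10.1 and give the precision as about 10.2% (normal approximation).
- If 37 is intended, correct the schema and give the precision as about 10.8% (normal approximation).
- If 42 is enrolment and 37 the number expected to be analysed, say so, state the attrition assumed, reconcile this with the statement in section 11.0 that all patients count for toxicity, and still give 10.8%.

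If the final analysis will use an exact interval, quote that width instead: about 11% for 42 or about 12% for 37.

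The cost is a wording change in one or two places and a slightly less favourable precision statement. No added patients are needed unless the sponsor wants the half-width held strictly at or below 10%, which would take 44 by the normal approximation.

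### Section 10.2 gives single-look stopping probabilities as if they were the chance of stopping under the whole rule, and does not say when a patient's outcome counts

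*Combined protocol and SAP*

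**What the plan says.** Section 10.2 sets the looks by enrolment: "these estimates will be made after every 5th enrolled patient to the study". The question at each look is whether "among patients receiving therapy, the true incidence of severe pneumonitis exceeds 15" percent. Evidence is sufficient when the estimate is one "whose lower 90% confidence limit exceeds 15" percent. Neither the sidedness nor the method of that limit is given.

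The criterion is turned into counts, with the denominator described only as the number observed: "pneumonitis of total number observed) would lead to exceeding such a limit: 3 or more of the first 5", then 4 of 10, 5 of 15 and 6 of 20. No count is listed beyond 20, although Section 10.1 plans 37 patients and the Schema 42.

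The stated properties of the rule are:
- True rate 10%: "the probability of stopping the study under these rules is less than 1% after enrollment of 5 patients on the study", then "<1.3% after enrollment of the first 10, and roughly <1% after enrollment of 20 patients on the study".
- True rate 20%: "If the true probability is 20%, then the probability of stopping after 5, 10, and 20 patients is 6%, 12% and 19%, respectively".
- True rate 40%: "the probability of stopping after 5, 10, and 20 patients is approximately 32%, 62%, and 88%, respectively".

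On timing, Section 7.0 (footnote a) puts the boost typically about two weeks after study entry. Sections 7.0 (footnote c), 8.2.1 and 11.0 follow toxicity for six months after the boost. Section 10.2 does not say how long a patient must be followed to count, or whether an earlier cohort's count can still trigger the rule at a later look.

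**The concern.** The figures are introduced as the chance of stopping under a rule with several looks. Each further look can only add to that chance, so a value that falls between 10 and 20 patients cannot be what the text calls it. Pneumonitis is the primary objective (Section 2.0) and this is its only formal stopping rule. Those who approve and monitor the trial would rely on these figures for two things: how often the rule halts an acceptably safe treatment, and how often it catches an unsafe one.

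The second question is timing. The looks are counted in enrolments, but the stated probabilities need all n outcomes. When a cohort's last patient enters, that patient has usually not yet been boosted.

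**Working it through.** **Inputs.** From Section 10.2: counts r = 3, 4, 5, 6 at n = 5, 10, 15, 20, and true rates p = 10, 20, 40%. From Section 7.0 footnote a: about two weeks from entry to boost. From Section 8.2.1: six months of toxicity follow-up.

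**1. Reproduce the plan's figures.** One look, all n outcomes known: P(X ≥ r) with X ~ Binomial(n, p).

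| True rate | 3/5 | 4/10 | 6/20 | Stated |
|---|---|---|---|---|
| 10% | 0.86% | 1.28% | 1.13% | <1, <1.3, roughly <1% |
| 20% | 5.8% | 12.1% | 19.6% | 6, 12, 19% |
| 40% | 31.7% | 61.8% | 87.4% | 32, 62, 88% |

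All nine agree within about one percentage point, so the stated figures are single-look tails.

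**2. Cumulative probability, complete outcomes.** Carry forward only the paths that have not stopped, add five patients, and sum the new crossings. Example at p = 20%, second look: the first five give 0, 1 or 2 events with probability 0.3277, 0.4096 and 0.2048. Reaching 4 then needs at least 4, 3 or 2 events in the next five (0.0067, 0.0579, 0.2627). The sum is 0.0022 + 0.0237 + 0.0538 = 0.0797, and the cumulative value is 0.0579 + 0.0797 ≈ 0.138.

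| True rate | First stop at 5, 10, 15, 20 | Cumulative at 5, 10, 20 |
|---|---|---|
| 10% | 0.0086, 0.0090, 0.0061, 0.0040 | 0.9, 1.8, 2.8% |
| 20% | 0.0579, 0.0797, 0.0678, 0.0557 | 5.8, 13.8, 26.1% |
| 40% | 0.3174, 0.3182, 0.1726, 0.0897 | 31.7, 63.6, 89.8% |

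At a true rate of exactly 15% the cumulative chance is 11.0% by 20 patients. It is 15.3% by 35, using the counts in step 4.

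**3. Look taken at the nth entry.** If the newest patient is not yet boosted, at most n − 1 outcomes are known. With the listed count at the first look, P(at least 3 of 4) = 4p³(1 − p) + p⁴:
- p = 20%: 4 × 0.008 × 0.8 + 0.0016 = 0.0272, or 2.7% (stated 6%).
- p = 40%: 4 × 0.064 × 0.6 + 0.0256 = 0.1792, or 18% (stated 32%).

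These are ceilings, because they credit the other four patients with complete follow-up. They need no assumption on accrual or onset.

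**4. Which limit, and the missing counts.** The one-sided exact 90% lower limit for x of n is the 10th percentile of Beta(x, n − x + 1). It is 0.247 at 3/5, 0.188 at 4/10, 0.172 at 5/15 and 0.166 at 6/20. One event fewer gives 0.112, 0.116, 0.122 and 0.127, so the listed counts are exactly the smallest that exceed 0.15. The lower end of a two-sided exact 90% interval would need 6/15 and 7/20 instead. The same one-sided limit gives 7/25 (0.163), 8/30 (0.162), 9/35 (0.162) and 10/40 (0.162); one event fewer stays below 0.15 each time. A one-sided normal-approximation limit and the lower end of a two-sided 90% Wilson interval give the same counts at every look to 35. The listed counts are therefore consistent with the exact method but do not prove that it was used.

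**The case against.** The strongest defence is that the rule itself works. Every listed count matches a one-sided exact 90% limit, and the single-look arithmetic is right. The number observed can fairly be read as the number with known outcomes; the per-look figures then hold, only later. The gap from ignoring earlier looks is about 2 points at a 40% rate. At 20% the plan understates its own protection, and false stopping of 2.8% at a 10% rate is still low. Section 11.0 requires 24-hour reporting of grade 4 or 5 toxicity attributable to radiation, and Section 9.0 lets several committees suspend accrual. All of this stands. It limits the harm but does not make the printed figures cumulative.

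A reader might infer more: that the plan promises a 32% chance of stopping at the moment of the fifth enrolment and can deliver only 18%, so that the rule is weaker than claimed. The documents do not support that.
- The explicit link to enrolment appears only in the 10% sentence. Its figures are upper bounds, and they are still met per look with n − 1 outcomes (0.37, 0.83 and 0.86%). The 40% sentence speaks only of patients.
- The 18% applies only if the look is taken at the fifth entry and the listed count is used. Under the lower-limit criterion itself, if three patients were boosted and fully followed, 2 of 3 would suffice (limit 0.196). That has probability 3 × 0.16 × 0.6 + 0.064 = 35% at a 40% rate.
- Even with the newest outcome always missing and no re-testing, cumulative stopping by 20 patients is 21% at a 20% rate, above the stated 19%. At 40% it is 86%, close to the stated 88%.
- The documents give no accrual rate or onset pattern, so the size of any delay cannot be derived from them.

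**Conclusion.** The point holds and should be fixed. The figures in Section 10.2 are not the chance of having stopped under the rule, however the number observed is read. The largest discrepancies are at 20 patients: 2.8% against roughly below 1% at a 10% rate, and 26% against 19% at a 20% rate. At 40% the difference is small (90% against 88%). These values assume independent outcomes with a common rate, complete outcomes in each cohort and looks at 5, 10, 15 and 20.

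The timing part is a missing definition, not a demonstrated loss of protection. If looks are taken at entry with the listed counts, stopping at the fifth patient is at most 2.7% at a 20% rate and 18% at 40%. If they wait for outcomes, the per-look figures are right but apply later. The two problems pull in opposite directions: ignoring earlier looks understates the stopping chance, while looking before outcomes are known reduces it at the early looks.

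**What to change.** Amend Section 10.2 as follows.

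1. Restate the probabilities as cumulative and as applying once each cohort's outcomes are complete. For 5, 10 and 20 patients: about 1, 2 and 3% at a 10% rate; 6, 14 and 26% at 20%; 32, 64 and 90% at 40%.
2. Define the cohorts as the first 5, 10, 15, 20 and so on patients who receive the boost, using the plan's existing six-month toxicity window. State that a cohort's count triggers the rule whenever it is reached, including at later looks as outcomes arrive.
3. State that the lower 90% limit is one-sided and exact. List the counts it gives at the remaining looks: 7/25, 8/30 and 9/35, plus 10/40 if the Schema's 42 patients stands. The 37 in Section 10.1 and the 42 in the Schema need to be reconciled first.

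The existing counts and the 15% threshold do not change. The cost is wording, plus a known six-month toxicity status for every boosted patient. Section 7.0 footnote g sets no strict visit schedule, so some patients may need an extra contact. The stated false-stopping figures become less favourable: 2.8% by 20 patients at a 10% rate, and about 11% by 20 and 15% by 35 if the true rate is exactly 15%. No accrual pause is added, so some patients will still be enrolled before earlier outcomes are known.
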